##### **2.4.6.1 Adverse events**

Pre-treatment adverse events are defined as those that have an onset date/time before the first infusion date/time of the patient. Treatment emergent adverse events are those that have an onset date/time in the treatment epoch. Any AE reported in the database with onset date after the end of the treatment epoch will be classified as post-treatment.

The epochs for safety analysis have been defined in [Section 2.1.5](#). Treatment-emergent adverse events will be presented for different periods under different treatment groups as follows (and as appropriate):

1. Adverse events started in PAP treatment epoch, by randomized treatment group.
2. Adverse events started in either PAP or in ETP while taking olipudase alfa. This will be presented by randomized treatment group as well as combined (ie, all patients treated with olipudase alfa).

### ***Generalities***

The primary focus of adverse event reporting will be on treatment-emergent adverse events. Pretreatment adverse events will be described separately.

If an adverse event date/time of onset (occurrence, worsening, or becoming serious) is incomplete, an imputation algorithm will be used to classify the adverse event as pretreatment, or treatment-emergent. The algorithm for imputing date/time of onset will be conservative and will classify an adverse event as treatment emergent unless there is definitive information to determine it is pretreatment. Details on classification of adverse events with missing or partial onset dates are provided in [Section 2.6.2](#). If an AE worsens in severity, two AEs of same verbatim but with different start/end dates and different severity are captured separately on the AE log page in the eCRF.

The AE log page in the eCRF captures the date when the event become serious. If and when this date is non-missing, it indicates that the AE started as non-serious and became serious at a later date. To account for non-serious and serious parts of the AE collected in one AE log page, this AE will be split into two AEs – one non-serious, and one serious AE – with the same AE number, with the following modifications in data for these two AEs:

- Non-serious AE: AE end date, AE outcome, date of death or hospitalization, autopsy information, criterion for serious adverse event (SAE) will be blank.
- Serious AE: AE start date will use the date the event became serious.

Action taken towards study drug and action taken toward AE will be considered in relation to the date the event became serious, the last infusion date and dosing information, and a determination will be made, in consultation with safety monitor of the trial, as to whether the recorded fields belong to non-serious AE or serious AE; then the decision will be implemented in analysis. Any such decision will be rationalized in the CSR.

The adverse events summary will be presented by SOC and PT sorted by the internationally agreed SOC order and decreasing frequency of PTs within SOCs within the olipudase alfa treatment arm, unless otherwise specified. Multiple occurrences of the same event in the same patient will be counted only once in the tables within a particular treatment phase. The denominator for computation of percentages is the safety population within each treatment group.

Start day of treatment emergent AE relative to first infusion = Start date of AE – first infusion date + 1

Start day of pre-treatment AE relative to first infusion = Start date of AE – first infusion date

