#### **Infusion associated reactions**

Protocol-defined infusion associated reactions (IAR): Any AE that occurs during the infusion or within up to 24 h after the start of the infusion and is considered related or possibly related to study treatment as judged by the investigator or the sponsor is defined as a protocol-defined IAR. An event occurring  $\geq 24$  h after the start of an infusion may be judged an IAR at the discretion of the investigator or sponsor. Sponsor identification will reconcile with investigator identification of IAR before the database lock as much as possible. It is, however, possible that the sponsor identifies an AE as an IAR which the investigator did not agree to be an IAR; in that case, the sponsor decision is deemed final.

For this study, IARs may present as hypersensitivity reactions, acute phase reactions (APR), and cytokine release syndrome (CRS).

IARs, specifically APRs and some hypersensitive reactions may be associated with changes in specific clinical laboratory parameters (see Section 10.4.1.3 of the study protocol), and will be reconciled with investigator identification of those events as marked in the AE log as appropriate, facilitated by periodic clinical/safety review of AEs.

Algorithm-defined IAR: All AEs that start between the start of infusion and the end of infusion plus 24 hours are defined as algorithm-defined IARs, irrespective of the perceived relation with study treatment. Any TEAEs with missing time but which happened on the same day or the day after the infusion will be considered as algorithm-defined IARs.

Pregnancy: Pregnancy of a female patient enrolled in the study as well as pregnancy occurring in female partner of a male patient enrolled in this study is captured as an adverse event of special interest. The eCRF provides urine pregnancy test results as positive or negative. Labs provide serum pregnancy test results. Pregnancy is entered in the database as an AE, and will be counted from the AE page.

Symptomatic overdose: This is captured as an adverse event in this study, and will be reconciled with the clinical review of dosing data. For details, please see Section 10.4.1.3 in the protocol. This will be counted from the AE page.

Laboratory values: The following laboratory values and symptoms will be considered AESIs:

- Any increase in AST, ALT, total bilirubin, or AP >3x baseline (prior to olipudase alfa therapy) and > ULN

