#### 2.4.6.1.1 *Treatment-emergent adverse events*

An overview of treatment-emergent adverse events (TEAEs) for PAP will be provided to include (potentially related is defined as either ‘related’ or ‘possibly related’ as assessed by the investigator):

- TEAEs
- TEAEs potentially related to study treatment
- TEAEs by severity
- TEAEs leading to treatment discontinuation
- TEAEs leading to study withdrawal
- TEAEs leading to dose reduction
- TEAEs leading to study treatment interruption
- Protocol-defined IARs
- Algorithm-defined IARs
- Treatment-emergent serious adverse events
- TEAEs with fatal outcome (deaths)
- Treatment-emergent pregnancies
- TEAEs which are considered symptomatic overdose
- Dose-limiting toxicities (collected in the adverse event log page in the eCRF, see protocol Section 8.1.6 for details)

The following summaries will be produced by primary SOC and PT:

- TEAEs
- TEAEs by severity (ie, mild, moderate, or severe)
- TEAEs potentially related to study treatment
- TEAEs potentially related to study treatment, by the worst severity (ie, mild, moderate, or severe)

The most common TEAEs are defined as those with percentages of events  $\geq 2\%$  and number of patients  $\geq 2$  in the olipudase alfa treatment group and in addition, the percentage of patients with the specific TEAEs in olipudase alfa treatment group is greater than placebo. The most common TEAEs by SOC and PT will be provided in descending order of olipudase alfa incidence, followed by placebo incidence.

Summary of TEAEs by the latest infusion dose immediately preceding the start of AE will be provided by SOC and PT.

Post-rescue PAP TEAEs by SOC and preferred term will be provided separately in a data listing using the rescue population.

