#### 2.4.6.1.2 *Adverse events of special interest*

**Protocol-defined IAR:** The following summaries will be produced by primary SOC and PT, and by treatment group for PAP:

- Protocol-defined IARs
- Protocol-defined IARs by the worst severity
- Protocol-defined IARs started during infusion
- Protocol-defined IARs started between 0 hours (exclusive) and 3 hours (exclusive) post end of infusion
- Protocol-defined IARs started between 3 hours (inclusive) and 24 hours (inclusive) post end of infusion
- Protocol-defined IARs started between 24 hours (exclusive) and 72 hours (inclusive) post end of infusion
- Protocol-defined IARs started after 72 hours post end of infusion

In case there are IARs identified by the sponsor (before database lock) that the investigator did not agree to be an IAR, sponsor-identified IARs may be added to the list of investigator-identified IARs to define the protocol-defined IARs, and additional summaries may be produced.

A subset of protocol-defined IARs will also be defined programmatically by searching for preferred terms within Hypersensitivity reaction SMQs (identified using SMQ code 20000214 Broad and Narrow scope). The summaries of Hypersensitivity IARs will be provided by primary SOC and PT.

**Algorithm-defined IAR:** Summary of algorithm-defined IARs by primary SOC and PT will be provided for PAP.

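### The SAP re-dates the serious half of a split adverse event and does not keep the original onset, so that record can be misplaced in the algorithm-defined IAR, onset-window and preceding-dose summaries

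*SAP*

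**What the plan says.** SAP 2.4.6.1 (Generalities) notes that "The AE log page in the eCRF captures the date when the event become serious" and uses this to turn one log entry into two records with the same AE number. For the first it says: "Non-serious AE: AE end date, AE outcome, date of death or hospitalization, autopsy information, criterion for serious adverse event (SAE) will be blank". The start date is not among the blanked fields, so the non-serious record keeps the true onset. For the second it says: "Serious AE: AE start date will use the date the event became serious".

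The start of the event is then used in three places:

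- SAP 2.1.5.1: "All AEs that start between the start of infusion and the end of infusion plus 24 hours are defined as algorithm-defined IARs". A companion rule covers absent times: "Any TEAEs with missing time but which happened on the same day or the day after the infusion will be considered as algorithm-defined IARs".
- SAP 2.4.6.1.2: a set of separate summaries by when the reaction started (during infusion, then windows cut at 3, 24 and 72 hours after its end), for example "Protocol-defined IARs started between 24 hours (exclusive) and 72 hours (inclusive) post end of infusion".
- SAP 2.4.6.1.1: "Summary of TEAEs by the latest infusion dose immediately preceding the start of AE will be provided by SOC and PT".

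Neither document says that the onset before the split is to be used in these derivations. The same SAP paragraph does arrange a case-by-case decision, using the became-serious date, the last infusion date and the dosing information, for the action-taken fields. IAR status, window and preceding dose get no such instruction.

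**The concern.** The date on which an event became serious suits the SAP's definition of treatment-emergence, which includes becoming serious. It does not suit questions about how an event relates in time to an infusion. Those depend on when the reaction began, which is known because the non-serious record holds it. A programmer who follows the text literally would work out infusion proximity and preceding dose for the serious record from the later date.

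IARs are adverse events of special interest here, and their timing carries meaning. Protocol 10.4.1.3 describes hypersensitivity reactions as typically early in or shortly after the infusion, and acute phase reactions as typically 12 to 72 hours after it. A reaction that began during an infusion and became serious two days later would have its serious record placed in the acute-phase time range. With about 18 patients per arm, one misplaced record is visible in a table row.

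**Working it through.** The plan states no figure on this point. The check follows a re-dated record through each definition.

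**Inputs.** Infusions last about 220 minutes outside Weeks 0 and 54 (Protocol 8.1.2) and are given every 2 weeks, ±3 days relative to Day 1 (Protocol 8.1.3.2). Scheduled doses in mg/kg from Week 0 to Week 16 are 0.1, 0.3, 0.3, 0.6, 0.6, 1.0, 2.0, 3.0, 3.0 (Protocol Table 1), then 3.0. About 36 patients are randomized 1:1, so 18 per arm.

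**Illustration.** Assume an event that starts 2 hours after the end of the Week 10 infusion (1.0 mg/kg) and is flagged as an IAR. The non-serious record is always an algorithm-defined IAR, window 0–3 h, dose 1.0. Hours from end of infusion for the serious record = 2 + lag. Clock times are used, with the next infusion exactly 14 days later.

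| Lag to seriousness | Hours after end of infusion | Algorithm-defined IAR | Window | Preceding dose (mg/kg) |
|---|---|---|---|---|
| 12 h | 14 | yes | 3–24 h | 1.0 |
| 24 h | 26 | no | 24–72 h | 1.0 |
| 48 h | 50 | no | 24–72 h | 1.0 |
| 96 h | 98 | no | >72 h | 1.0 |
| 10 days | 242 | no | >72 h | 1.0 |
| 14 days | 2 h after the Week 12 infusion | yes, for that infusion | 0–3 h | 2.0 |

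With the original onset, every row would read: yes, 0–3 h, 1.0.

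**Loss of algorithm-defined status.** From about a day onward the serious record falls outside the end-plus-24-hours limit. At a lag of 24 hours it would remain an algorithm-defined IAR if only a date were held, under the next-day rule. At 48 hours it would not.

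**False gain.** An event that began days before an infusion and becomes serious on the infusion day or the next day is counted as an algorithm-defined IAR if no time is held. If a time is held, it is counted whenever that time lies between infusion start and end plus 24 hours. Its known onset would show otherwise.

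**Second window.** The once-per-patient counting rule works within a table, and the onset windows are separate summaries. If the serious record inherits the IAR flag, which the SAP does not settle, one event appears in two of them. If only a date is held, nothing says which hour-based window the record enters.

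**Preceding dose.** The preceding infusion changes only if another infusion falls between onset and seriousness. The gap is nominally 14 days, and 14 − 6 = 8 to 14 + 6 = 20 days with both windows used. The dose must also differ. Weeks 0 to 16 contain 8 steps, of which 5 change dose (0.1→0.3, 0.3→0.6, 0.6→1.0, 1.0→2.0, 2.0→3.0). Weeks 16 to 52 contain (52 − 16)/2 = 18 steps and no scheduled change. That is 5 of 26, absent rechallenge or dose modification.

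**Weight of one patient.** 1/18 = 5.6 percentage points in a nominal arm. This is not a forecast of how often the problem occurs.

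**The case against.** The other side has several good points.

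- The became-serious date is a deliberate convention. The SAP speaks of "If an adverse event date/time of onset (occurrence, worsening, or becoming serious) is incomplete", and its treatment-emergent definition includes becoming serious. Worsening in severity is likewise held as two records with different start dates. This stands for treatment-emergence and SAE dating, and the fix leaves it alone. It does not answer which date the infusion-related derivations should use.
- Protocol-defined IARs rest on investigator or sponsor judgement and an eCRF flag, and an event 24 hours or more after the start of infusion may still be called one. This stands: their status is not computed from the re-dated start.
- Algorithm-defined IARs are over-inclusive by design, and SAP 2.6.2 counts ambiguous timing as an IAR. That is a sound default where timing is unknown. Here the onset may be known and would be ignored.
- That the form holds only a date of seriousness is an inference. One sentence mentions a date, another a date/time, and the eCRF is not among the documents. This stands, which is why both cases are worked through above.
- A later dose is not always a higher one. Under Protocol 8.1.3.3 a related moderate event leads to a repeat of the dose and a related severe event to a decrease. This stands and narrows the dose effect further.

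A reader might infer that the rule cuts the link between a serious reaction and its infusion. The documents do not support that. No planned table crosses seriousness with onset window or dose, and SAP 2.4.6.1.4 tabulates SAEs by system organ class and preferred term only. Protocol 11.5.5.1 requires SAE listings with the dose before or during the event, SAP 2.5 requires a narrative for every SAE and every protocol-defined IAR, and both records share an AE number.

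**Conclusion.** The rule is wrong as written for three derivations, in a limited way. For the serious record only:

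- algorithm-defined IAR status can be lost or falsely gained;
- a protocol-defined IAR can enter a second, later onset window if the flag is carried over;
- the preceding-dose row can be wrong, but only when an infusion at a different dose intervenes (5 of 26 scheduled steps in the primary analysis period, none after Week 16).

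It would go too far to say that infusion-reaction status, window and dose are all taken from the wrong date. Protocol-defined status is not derived this way, the non-serious record keeps the true onset, and overall patient-level IAR counts survive except for false algorithm-defined IARs. The conclusion assumes a literal reading of the SAP and no further programming specification. The documents give no count of events that became serious after onset, so the number affected cannot be estimated. Safety analysis is descriptive, and no hypothesis test depends on this.

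**What to change.** In SAP 2.4.6.1, state that both records of a split event carry the original onset date and time and the investigator or sponsor IAR flag. State that these are used for algorithm-defined IAR status, the onset windows of 2.4.6.1.2 and the preceding-dose summary of 2.4.6.1.1. Keep the became-serious date for treatment-emergence, period assignment and SAE dating. Count records that share an AE number as one event wherever events are counted. Because an event that began before the first infusion can become treatment-emergent through seriousness, also say how the dose summary shows an event with no infusion before its onset.

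The cost is a few sentences in the SAP and an extra onset date/time variable, plus the carried-over flag, in the adverse-event dataset. The original onset is already held on the non-serious record, so no new data collection is needed.

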#### 2.4.6.1.1 *Treatment-emergent adverse events*

An overview of treatment-emergent adverse events (TEAEs) for PAP will be provided to include (potentially related is defined as either ‘related’ or ‘possibly related’ as assessed by the investigator):

- TEAEs
- TEAEs potentially related to study treatment
- TEAEs by severity
- TEAEs leading to treatment discontinuation
- TEAEs leading to study withdrawal
- TEAEs leading to dose reduction
- TEAEs leading to study treatment interruption
- Protocol-defined IARs
- Algorithm-defined IARs
- Treatment-emergent serious adverse events
- TEAEs with fatal outcome (deaths)
- Treatment-emergent pregnancies
- TEAEs which are considered symptomatic overdose
- Dose-limiting toxicities (collected in the adverse event log page in the eCRF, see protocol Section 8.1.6 for details)

The following summaries will be produced by primary SOC and PT:

- TEAEs
- TEAEs by severity (ie, mild, moderate, or severe)
- TEAEs potentially related to study treatment
- TEAEs potentially related to study treatment, by the worst severity (ie, mild, moderate, or severe)

The most common TEAEs are defined as those with percentages of events  $\geq 2\%$  and number of patients  $\geq 2$  in the olipudase alfa treatment group and in addition, the percentage of patients with the specific TEAEs in olipudase alfa treatment group is greater than placebo. The most common TEAEs by SOC and PT will be provided in descending order of olipudase alfa incidence, followed by placebo incidence.

Summary of TEAEs by the latest infusion dose immediately preceding the start of AE will be provided by SOC and PT.

Post-rescue PAP TEAEs by SOC and preferred term will be provided separately in a data listing using the rescue population.

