During the PAP, one rechallenge each will be allowed for doses administered at Week 0 (0.1 mg/kg olipudase alfa or placebo) and at Week 4 (0.3 mg/kg olipudase alfa or placebo). Patients who are unable to tolerate the rechallenge at those doses will be discontinued from the study. If a patient is discontinued due to inability to tolerate rechallenge (ie, a second dose of 0.3 mg/kg olipudase alfa), then an additional patient may be randomized. Any patient who successfully dose-escalates through Week 4, but cannot tolerate study drug infusions at later weeks, will continue in the trial at the Week 4 dose (ie, 0.3 mg/kg olipudase alfa or placebo) until end of study; likewise, any patient unable to tolerate a dose administered during later weeks will receive the HTD even if that dose is less than the target randomized dose and will continue in the ETP at this dose. The minimum active dose administered will be 0.3 mg/kg olipudase alfa.

During the ETP, the same dose-escalation conditions will apply for patients who cross over from the placebo arm during the PAP to the active treatment arm, except that patients unable to tolerate the rechallenge allowed each at Week 54 (0.1 mg/kg olipudase alfa) and at Week 58 (0.3 mg/kg olipudase alfa) will discontinue from the study and will not be replaced.

During the PAP and ETP, in-patient hospitalization will be required preinfusion and for at least 24 hours after the infusion during dose escalation (ie, through Week 16 and Week 70, respectively) and may be required at the quarterly and yearly visits up through the end of Year 2; in-patient hospitalization may be necessary during quarterly and yearly study visits in Years 3 through 5. For all other infusions, patients will be monitored for safety in the clinic for at least 1 hour. All patients will have an end of study/early discontinuation visit within 2 weeks after the last infusion of study treatment. In addition, all patients will receive a follow-up phone call for safety approximately 30 to 37 days after the last infusion of study drug.

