8.1.1 Treatments administered

The term “study drug” will refer to olipudase alfa and placebo (saline [0.9% sodium chloride solution]), but only olipudase alfa is an IMP.

During clinical development of olipudase alfa, incremental changes were made to the olipudase alfa manufacturing process. The different processes are referred to as Process B, C(■) and C(■).

Dosing with study drug will be by intravenous infusion every 2 weeks (± 3 days) in reference to the date of the first infusion (Day 1) for each patient. The 52-week treatment period of the PAP will begin on Day 1 with the first infusion of study drug.

To maintain the double-blind, all patients regardless of treatment assignment will undergo dose escalation under the same conditions and according to the schedule provided in [Table 1](#).

All infusions will take place in a monitored setting with ready access to emergency resuscitation equipment and medications (see [Section 10.1](#) for information on timing for in-patient hospitalization). One rechallenge each will be allowed for doses administered at Week 0 (0.1 mg/kg olipudase alfa or placebo) and at Week 4 (0.3 mg/kg olipudase alfa or placebo). Patients who are unable to tolerate the rechallenge at those doses will be discontinued from the study. If a patient is discontinued due to inability to tolerate rechallenge, (ie, a second dose of 0.3 mg/kg olipudase alfa), then an additional patient may be randomized but only during the PAP. During the PAP and ETP, in-patient hospitalization will be required preinfusion and for at least 24 hours after the infusion during dose escalation (ie, through Week 16 and Week 70, respectively) and may be required at the quarterly and yearly visits up through the end of Year 2; in-patient hospitalization may be necessary during quarterly and yearly study visits in Years 3 through 5.

Home infusion may be initiated during COVID-19 (ETP) by trained home nurses every 2 weeks (± 3 days), if agreed between the investigator and the sponsor, in compliance with applicable country-specific regulations. Patients must meet specific eligibility requirements ([Section 10.1.1](#)). Patients who initiated home infusion during the COVID-19 pandemic, and continue to be on home infusion, may continue receiving home infusion by trained home nurses in the ETP every 2 weeks (± 3 days) until the end of the ETP (refer to [Appendix B](#) for Germany).

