8.1.3.3 Escalation schema

See [Table 1](#) and [Figure 1](#) for the dose escalation schedule and algorithm, respectively. During dose escalation (PAP and ETP), patients will be admitted to the hospital as described in [Section 10.1](#).

Table 1 - Dose escalation scheme during the PAP

Study week PAP ^a	Scheduled study drug ^b dose	
Week 0 ^c	0.1 mg/kg	
Week 2	0.3 mg/kg	
Week 4 ^c	0.3 mg/kg	
Week 6	0.6 mg/kg	
Week 8	0.6 mg/kg	
Week 10	1.0 mg/kg	
Week 12	2.0 mg/kg	
Week 14	3.0 mg/kg	
Week 16	3.0 mg/kg	End of the mock dose escalation for patients assigned to placebo; end of true dose escalation for patients assigned to target dose 3.0 mg/kg.

a Study weeks do not account for rechallenges.

b Study drug means olipudase alfa and placebo.

c A rechallenge will be permitted only once at Week 0 and at Week 4.

[figure not shown]
The same dose-escalation schedule and conditions will apply for patients who cross over from the placebo arm during the PAP to the active treatment arm in the ETP, except that patients unable to tolerate the 1 rechallenge each allowed for doses administered at Week 54 (0.1 mg/kg olipudase alfa) and Week 58 (0.3 mg/kg olipudase alfa) will discontinue from the study and will not be replaced.

The following criteria will determine the next dose of study drug to be administered, provided the patient does not experience an AE that meets the DLT ([Section 8.1.4](#)). Only AEs not related to the patient's underlying condition will affect dose escalation. These criteria apply to AEs considered related to study treatment:

1. If the patient experiences no AE or a mild AE, escalate to the next dose.
2. If the patient experiences a moderate AE, repeat the same dose.
3. If the patient experiences a severe AE, decrease to the prior dose.

If a patient presents on the day of infusion either with an unresolved AE or an acute illness, neither of which meets the patient DLT criteria ([Section 8.1.4](#)), then study drug infusion may be withheld or administered at the discretion of the investigator. If it is not possible to administer a regularly scheduled infusion within the 3-day window allowed per protocol, see [Section 8.1.3.2](#).

Figure 1 - Dose escalation algorithm

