## 1.5 MODIFICATIONS TO THE STATISTICAL SECTION OF THE PROTOCOL

This section summarizes discrepancies between the statistical analysis described in the amended DFI12712 protocol 11, dated 12 August 2019, and this SAP.

- The following language about the summary of immune response assessments in the protocol Section 11.5.5.4 will not be provided by the dose level of the infusion before or during the evaluation, since the infusion information will be included in the data listing.  
*The presence, absence, and titers of serum anti-olipudase alfa IgG antibodies and routine levels of acute phase reactants will be summarized over time overall and by the dose level of the infusion before or during the evaluation.*
- The following language about the exploratory pharmacodynamic analyses in the protocol Section 11.5.6.2 is not planned in this SAP but may be done ad hoc if deemed necessary.  
*Exploratory correlation analyses will be attempted to evaluate relationships between different PD markers and between sphingomyelin and /or lysosphingomyelin levels from different sources.*
- Multiplex assay of inflammatory and vascular biomarkers are analyzed as both exploratory efficacy and safety endpoints in the protocol but will be treated only as safety endpoints in this SAP.
- The ETP population mentioned in the protocol Section 11.4 was removed from the SAP, since data for PAP+ETP will be analyzed in a cumulative way.
- The annualized rate of TEAEs and separate analyses of AEs by demographic characteristics (eg, age and sex) mentioned in the protocol Section 11.5.5.1 will be presented in the integrated summary of safety and will not be done in the study SAP.

- Protocol Section 11.5.6.3 for pharmacokinetic-pharmacodynamic analyses will not be done at the study level, but may be conducted using pooled data from different clinical studies and the results may be included in a separate report.
- For the summary of exposure, the protocol mentioned using the safety population. However, the population was changed to mITT population in the SAP in order to accurately summarize the duration of exposure prior to rescue therapy for patients who were randomized to placebo at the beginning.

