#### **2.4.4.2 Compliance**

Compliance to the treatment regimen will be monitored in terms of the percentage of scheduled infusions the patient receives during the treatment periods, irrespective of whether the infusion was total or partial. This is calculated as:

$100 \times (\text{number of infusions received}) / (\text{number of infusions intended to be received})$

For PAP, the number of infusions intended to be received is 27 over 52 weeks for a patient who complete PAP.

Noncompliance in PAP is defined as missing 2 or more consecutive infusions in PAP (excluding for cause misses, such as when the missed doses are required by the protocol due to a DLT) or 4 or more infusions in total in the 52-week PAP treatment period.

Noncompliance in PAP+ETP is defined as missing 4 or more infusions in every 52-week period following PAP treatment period until the end of study.

Treatment compliance for overall PAP will be summarized descriptively as quantitative variable using mITT population and randomized treatment group.

The percentage of patients whose compliance is  $\leq 85\%$  (missing 4 or more infusions out of scheduled 27 infusions in PAP) will be provided. In addition, number and percentage of patients with noncompliance, and by reasons (missed 2 or more consecutive infusions not for cause (“not for cause” means there is no justifiable reasons for a missed dose, eg., DLT), or missed 4 or more infusions in total in the 52-week PAP) will be provided.

Similar summaries will be provided for PAP+ETP.

A case of overdose will be reported as an AE and will be summarized with AE. An overdose is defined in Section 10.4.1.3 of the protocol.

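### The adverse-event table by preceding dose has no stated denominator, counting rule or exposure measure, and under the SAP's general rules it reflects the infusion schedule rather than tolerability at each dose

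*SAP*

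**What the plan says.** Among the treatment-emergent adverse event (TEAE) displays, SAP 2.4.6.1.1 lists: "Summary of TEAEs by the latest infusion dose immediately preceding the start of AE will be provided by SOC and PT". That sentence is the whole specification. It does not name a denominator, say whether one patient can appear at several doses, attach any exposure measure to a dose, or say whether the extension treatment period (ETP) is included.

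Two general rules in SAP 2.4.6.1 (Generalities) would fill the gap. On counting: "Multiple occurrences of the same event in the same patient will be counted only once in the tables within a particular treatment phase". On percentages: "The denominator for computation of percentages is the safety population within each treatment group".

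On dosing, Protocol 8.1.1 states: "Dosing with study drug will be by intravenous infusion every 2 weeks". Table 1 in Protocol 8.1.3.3 ("Dose escalation scheme during the PAP") sets the dose for Weeks 0 to 16, ending at 3.0 mg/kg. SAP 2.4.4.2 gives the total: "For PAP, the number of infusions intended to be received is 27 over 52 weeks for a patient who complete PAP".

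Other sections do not supply what is missing:
- SAP 2.4.4.1 summarizes exposure as duration, cumulative milligrams, and the patients who did not reach, or later came down from, the target dose.
- SAP 2.4.6.1.2 breaks infusion-associated reactions (IARs) down by treatment group, severity and time since infusion, not by dose.
- SAP 1.5 sends "The annualized rate of TEAEs and separate analyses of AEs by demographic characteristics" to the integrated summary of safety.

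No section gives patients treated, infusions given or event rates by dose level.

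**The concern.** A reader will use a table of events by preceding dose to see how each escalation step was tolerated. That matters here: Protocol 9.7 explains that escalation exists to avoid a large release of ceramide, and the amendment history in Protocol Appendix C reports that in the Phase 1b study reactions were more frequent on starting 0.6 mg/kg.

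The steps are given once or twice and the target dose many times. A count of patients with an event at each dose therefore accumulates at the dose given longest. A poorly tolerated step could look mild beside the maintenance dose, and the planned outputs would not let a reader recover the exposure needed to correct the impression.

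**Working it through.** **Inputs from the documents.** Infusions every 2 weeks from Week 0 to Week 52 of the primary analysis period (PAP); doses by week from Table 1; no repeats, rechallenges, missed doses or reductions.

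**Reproducing the plan's figure.** 0.1 mg/kg at Week 0 (1 infusion); 0.3 at Weeks 2 and 4 (2); 0.6 at Weeks 6 and 8 (2); 1.0 at Week 10 (1); 2.0 at Week 12 (1); 3.0 at Weeks 14 to 52 (20). Total 1 + 2 + 2 + 1 + 1 + 20 = 27, which agrees with SAP 2.4.4.2. In time at risk up to the Week 54 infusion, 3.0 mg/kg has 20 × 2 = 40 weeks and a dose given once has 2 weeks.

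**Assumption, not in the documents.** A given preferred term (PT) has the same risk p at every infusion and every dose, independently between infusions. There is then no dose effect to find. A range of p is shown.

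**Reading A: a patient is counted once per dose level.** The expected share of patients at a dose given n times is 1 − (1 − p)^n.

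| p | Dose given once | Dose given twice | 3.0 mg/kg (n = 20) | Ratio, 3.0 to a dose given once |
|---|---|---|---|---|
| 1% | 1.0% | 2.0% | 18.2% | 18.2 |
| 2% | 2.0% | 4.0% | 33.2% | 16.6 |
| 5% | 5.0% | 9.8% | 64.2% | 12.8 |
| 10% | 10.0% | 19.0% | 87.8% | 8.8 |

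If delays leave only 12 infusions at 3.0 mg/kg, p = 5% still gives 1 − 0.95^12 = 46.0% against 5.0%.

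Reading A can also invert a real difference. With a true risk of 10% per infusion at 2.0 mg/kg and 2% at 3.0 mg/kg, the table would show 10% against 1 − 0.98^20 = 33.2%.

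**Reading B: only the first occurrence in the PAP is counted.** With k infusions before the dose level, the expected share is (1 − p)^k × [1 − (1 − p)^n]. For 0.1 mg/kg, k = 0 and n = 1; for 2.0 mg/kg, k = 6 and n = 1; for 3.0 mg/kg, k = 7 and n = 20.

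| p | 0.1 mg/kg | 2.0 mg/kg | 3.0 mg/kg |
|---|---|---|---|
| 1% | 1.0% | 0.9% | 17.0% |
| 5% | 5.0% | 3.7% | 44.8% |
| 10% | 10.0% | 5.3% | 42.0% |
| 20% | 20.0% | 5.2% | 20.7% |
| 30% | 30.0% | 3.5% | 8.2% |

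Setting (1 − p)^7 × [1 − (1 − p)^20] = p gives p of about 20.3%. Above that, 0.1 mg/kg shows more than 3.0 mg/kg.

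**After the change.** With the same equal risk, infusions with at least one event per 100 infusions given has expected value 100p at every dose. For p = 5% that is 5.0 per 100 at all six levels, a ratio of 1.0.

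**The case against.** The strongest reply is that the sentence in 2.4.6.1.1 sets no denominator, no percentage and no counting rule, and that the general denominator is written for treatment-group columns, not dose columns. A reader might infer that the SAP prescribes dividing by the whole arm in this table. It does not say so; that follows only by default. This part stands, and the silence is itself something to correct. Switching to patients who received the level would not remove the confounding, because 20 infusions would still be set against 1.

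A reader might also infer that 3.0 mg/kg must look worst, by about 13-fold. That figure needs Reading A and an assumed 5% risk. Under Reading B the excess is smaller, and for very frequent events it reverses against 0.1 mg/kg. Keeping patients who never reached 3.0 mg/kg in its denominator also lowers the 3.0 mg/kg figure somewhat.

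Nor would a poorly tolerated step go unseen altogether. SAP 2.4.4.1 reports failure to reach or keep the target dose. SAP 2.4.6.1.1 includes dose-limiting toxicities and events leading to reduction or interruption. SAP 2.4.6.1.5 to 2.4.6.1.7 list events leading to discontinuation, reduction or interruption with the dose concerned. None of these is an event rate by dose.

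Finally, moving the annualized rate to the integrated summary did not cause this gap. Protocol 11.5.5.1 planned that rate for the overall analyses of adverse events, not by dose level, so restoring it would not repair this table.

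**Conclusion.** The point holds in this form: the by-dose table is under-specified, and on either reading of the general counting rule it mixes dose with the number and order of infusions. The 20-to-1 schedule comes from the documents. The percentages rest on assumed risks that are equal and independent across infusions. Over 1% to 10% per infusion, no true dose effect would show as 1% to 10% at a dose given once and about 18% to 88% at 3.0 mg/kg (Reading A). Under Reading B at 5%, it would show as 5.0% at 0.1 mg/kg and 44.8% at 3.0 mg/kg. Events unrelated to infusion accrue with time and meet the same imbalance, 40 weeks against 2. If the table extends into the ETP, exposure at 3.0 mg/kg grows further. Actual infusion counts will vary with repeats, missed doses, lower tolerated doses and rescue.

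The consequence is limited to interpretation of tolerability by dose. SAP 2.4.6 makes safety analysis essentially descriptive, and no formal test or dosing rule is stated to use this table.

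**What to change.** In SAP 2.4.6.1.1, and correspondingly for protocol-defined IARs in 2.4.6.1.2, specify for each dose level:
- a patient is counted once per PT per dose level;
- the denominator is the patients who received that level;
- the number of infusions given at that level is shown;
- the rate is infusions with at least one event per 100 infusions, with patient-time shown for events not related to infusion;
- the period covered (PAP, or PAP and ETP) is stated.

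Count infusions with at least one event rather than events, because Protocol 10.4.2 requires each symptom of an IAR to be recorded separately, so one reaction could otherwise count several times. Add a note that Protocol 8.1.3.3 repeats a dose after a moderate related event, so infusions per level depend partly on outcome and the rates remain descriptive. Placebo at the matching mock-escalation visits would be a useful comparison but is optional.

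The cost is SAP wording and one additional table. Dose, infusion and onset data are already collected, and neither trial conduct nor blinding changes.
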